12.6 Second Primary Malignancies

Second primary malignancies (SPM) will be monitored as events of interest and must be reported as SAEs. This includes any second primary malignancy, regardless of causal relationship to any study drug, occurring at any time for the duration of the study, from the time of signing informed consent until 5 years after registration in the trial or until completion of maintenance therapy for patients who are still on maintenance at 5 years after registration.

Events of second primary malignancy are to be reported using the SAE report form and must be considered an "Important Medical Event" even if no other serious criteria apply. Documentation on the diagnosis of the second primary malignancy must be provided at the time of reporting as a serious adverse event (e.g. pathology report).

A SAE form should be filled out and send to HOVON Data Center as is described in section 12.3.1. SPM must also be documented in the other appropriate page(s) of the CRF (e.g. Adverse Event Form and Follow up Form).

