Venetoclax has been approved for treatment of patients with CLL and del(17p), with a manageable safety profile as long as precautions concerning the risk of tumor lysis syndrome are followed as stated for this trial. Several hundreds of patients have been treated with the combination of ibrutinib and venetoclax in clinical trials, no unexpected safety signals differing from the safety profile described for each drug have been reported. However, data on long term safety and the outcome upon stopping treatment is still immature, thus the current study especially addresses these aspects in addition to the primary endpoint.

Consequently, the aim of the current trial is to evaluate if combination treatment with venetoclax + ibrutinib in patients with RR CLL can lead to MRD negativity, which may induce long lasting remissions for those patients randomized for observation after cycle 15.

Planned interim analysis and DSMB

The interim analyses of the trial are described in section 14.4.4.

Real time monitoring of the outcome for patients randomized for stopping treatment will continue based on the MRD results. MRD data will be collected at the 2 central laboratories and shared with central data management.

4 Investigators and study administrative structure

Responsibility	Name	Affiliation/Address
Sponsor	HOVON	VU University Medical Center, [name] The Netherlands [contact]
Co-sponsor	NCLLSG	Rigshospitalet, Copenhagen University Hospital Department of Hematology, Building 4042 [name] Denmark [contact]
Representative of Sponsor (HOVON)	[name], chairman [name], treasurer	Erasmus MC, Rotterdam Radboud University, Nijmegen
Principal Investigator	[name]	Copenhagen University hospital, Rigshospitalet Department of Hematology, building 4042 [name] , Denmark [contact] Mail: [contact]
	[name]	Academic Medical Center University of Amsterdam Department of Hematology F4-224 [name], The Netherlands [contact] Mail: [contact]
Co-investigators	[name]	Albert Schweitzer hospital Department of Internal Medicine [name], The Netherlands [contact] Mail: [contact]
	[name]	Uppsala University Hospital [name], Sweden [contact] Mail: [contact]

Coordinating investigator	The Netherlands	
	[name]	Academic Medical Center, Amsterdam
	Denmark	

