10.1 Time of clinical evaluations

- Before enrollment: within 28 days before registration, as specified in 10.2
- After each cycle until end of cycle 15
- Weekly during venetoclax ramp up in cycle 3
- After cycle 15: every 3 months for 2 years and every 4 months for the 3rd year, whether in the maintenance or the treatment cessation group, until month 51 (15 months + 3 years)
- Thereafter every 6 months until 7 years after registration or until progression, whatever comes first.

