10.1.1 Follow up

All patients will be followed until 7 years after registration.

To be able to collect long term follow up data until patient`s death after the end of this study, inclusion in a country specific registry (e.g. the Danish National CLL register or the Dutch Pharos registry or registry of the other Nordic countries) is strongly recommended. For this purpose, each patient will be informed about the importance of long term follow-up data and asked for his/her consent to the long term follow-up within an appropriate registry. For patients with a written informed consent for the registry, data for overall survival, late toxicities such as secondary malignancies, further treatments and the course of the disease will be collected after the end of the trial.

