14.4.4 Interim analysis

No interim analysis on the primary endpoint is planned.

Draft outline of interim analyses in the study:

Analysis	Time point	Analysis	Impact on primary endpoint
Analysis IA	First 15 pt. after induction cycle 3	Interim analysis on safety	No, only safety
Analysis IB	First 10 pt. with low CrCl 30-50. After induction cycle 3.	Interim analysis on safety	No, only safety
Analysis II	first 23 pt. reaching MRD negativity at cycle 9 or first 51 pt. at cycle 9, which occurs first	Interim analysis on safety and efficacy	No impact, prior to randomization
Analysis III	15 pt. randomized for stopping treatment after cycle 15 or first 51 pt. at end of cycle15, which	Interim analysis on safety and efficacy	No impact, at time of randomization

	occurs first		
Analysis IV	6 months after first 15 pt. randomized for stopping treatment at cycle 15 or 6 months after first 51 pt. at cycle 15, which occurs first	Interim analysis on efficacy	Post randomization, MRD positivity and primary are dependent. No correction.
Analysis V	12 months after 15 pt. randomized for stopping treatment at cycle 15 or 12 months after first 51 pt. at cycle 15, which occurs first	Interim analysis on efficacy	Post randomization, MRD positivity and primary are dependent. No correction
Analysis VI	Last patient reaching Month 27	Primary end point analysis	
Analysis VII	Last patient reaching 7 years	Update final analysis	

In the Interim analyses on safety (IA and IB), , the incidence of (serious) adverse events, death, creatinine level, AEs of special interest (atrial fibrillation, bleeding events and TLS) and progression according to appendix B and MRD positivity, will be reported. These analyses will be before the randomization stage and patients have not been assigned to any of the arms.

In Interim analysis on safety and efficacy and In Interim analysis on efficacy, the incidence of (serious) adverse events, death, creatinine level, number of assigned patients at each treatment arm, number of progression, best response, number of reinitiated patients (if applicable), AEs of special interest (atrial fibrillation and bleeding events), TLS)and progression according to appendix B and MRD positivity, will be reported.

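### Any-cause reporting of second primary malignancies ends at 5 years unless the patient is still on maintenance, although follow-up and the last analysis run to 7 years, so late cases off treatment are under-counted

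*Protocol*

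**What the plan says.** Section 12.6 treats second primary malignancies as serious adverse events regardless of causal relationship, "occurring at any time for the duration of the study, from the time of signing informed consent", and in the same sentence ends the window: "until 5 years after registration in the trial or until completion of maintenance therapy for patients who are still on maintenance at 5 years". Section 9.3 labels maintenance as not for arm B.

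The study runs longer than that. Section 10.1.1: "All patients will be followed until 7 years after registration". Section 10.1 sets the visits after month 51: "Thereafter every 6 months until 7 years after registration or until progression, whatever comes first". In section 14.4.4, Analysis VII, the update of the final analysis, is timed at "Last patient reaching 7 years". Section 18.4 ends the study at the last patient's last visit.

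The general rule in section 12.3.1 closes serious adverse event reporting 30 days after the last protocol dose, or earlier if another systemic therapy for the disease starts. Later events are reportable if at least possibly related. Section 14.4.2 tabulates toxicity after cycle 15 separately for MRD-positive patients, arm A and arm B. The Synopsis states the interest in late safety: "data on long term safety and the outcome upon stopping treatment is still immature, thus the current study especially addresses these aspects".

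**The concern.** Second malignancy is a slow risk, and years 5 to 7 are part of what the long follow-up can add. Under section 12.6 as written, whether a malignancy in those years must be reported depends on whether the patient is still on maintenance. The end of the observation window is therefore tied to treatment. A table by group at the 7-year update could then show more malignancies under continuous ibrutinib than after stopping even if the true risks were equal. A reader interested in the safety of stopping would be misled in favour of stopping. What is at stake is the descriptive long-term safety comparison, not the efficacy conclusion.

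**Working it through.** **1. Who must report a second malignancy in years 5 to 7**

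- Arm A or non-randomized, still on ibrutinib maintenance: any cause, under the extension in 12.6 (and under 12.3.1 while on drug).
- Arm A or non-randomized, stopped ibrutinib before year 5: the 12.6 window closes at year 5. After that, only events at least possibly related, once 30 days have passed since the last dose.
- Arm B, untreated: the 12.6 window closes at year 5 and the extension cannot apply (9.3). After that, only events at least possibly related.
- Arm B, re-treated and on ibrutinib (9.4): not called maintenance, but inside the 12.3.1 window until 30 days after the last dose.

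The uncovered set is malignancies judged unrelated or unlikely in patients off treatment.

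**2. Other routes of capture**

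- Table 10.2.1 marks adverse events after month 51, but section 12.2.1 applies the same 30-day and relatedness limits to adverse events.
- Section 12.6 also sends second malignancies to the Follow up Form, but it does not say that this continues past its own window.
- The registry in 10.1.1 needs separate consent, and its data on "late toxicities such as secondary malignancies, further treatments and the course of the disease will be collected after the end of the trial" do not clearly cover years 5 to 7 of the trial.

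**3. Arm sizes**

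Section 14.1 gives 62 patients in arm B with at least 44 progression free. An exact binomial search at 60% against 75% returns the same rule (n = 62, r = 44, one-sided alpha 0.0492, power 0.812). With 1:2 allocation, 62 × 3/2 = 93 randomized, so arm A has 31.

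**4. Size of the gap**

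The protocol gives no malignancy rate, no share still followed and no retention on maintenance. All three are assumed here.

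- Share of follow-up outside the 5-year window: (7 − 5)/7 = 28.6%.
- Arm B person-years outside, with 70 to 90% followed and untreated: 62 × 0.70 × 2 = 86.8 to 62 × 0.90 × 2 = 111.6.
- Arm B cases outside the any-cause rule, at 1 to 3 per 100 person-years: 86.8 × 0.01 = 0.9 to 111.6 × 0.03 = 3.3.
- Arm A person-years also outside: 31 × 0.70 × 2 × (1 − 0.80) = 8.7 to 31 × 0.90 × 2 × (1 − 0.40) = 33.5.

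**5. Apparent contrast with equal true risk**

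Take m as the share of arm A on maintenance through year 7, give arm B no coverage after year 5, and divide both groups by 7 years from registration. The apparent ratio of A to B is (5 + 2m)/5.

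- m = 0.40: 5.8/5 = 1.16
- m = 0.60: 6.2/5 = 1.24
- m = 0.80: 6.6/5 = 1.32

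**The case against.** The strongest reply is that 12.6 is generous. For untreated patients it adds any-cause reporting out to 5 years, where the general rule would stop 30 days after the last dose. A longer safety window on treatment is the protocol's normal rule. The sentence can also be read with the 5-year limit simply defining the reporting period, so the 5 years may be deliberate. That reading is fair, but it does not remove the mismatch with 7-year follow-up or the dependence on treatment.

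A reader might infer that late malignancies are lost selectively in the stopping arm. The text does not support that. The cut-off follows treatment status at year 5, so patients of any group who stopped ibrutinib are cut off. Possibly related cases, and cases in re-treated arm B patients on ibrutinib, stay reportable. Arm B is the most affected group, not the only one.

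A reader might also infer a spurious ratio of about 1.4, which is 7/5. That needs every arm A patient on ibrutinib through year 7, no late arm B case reported by any route, and equal 7-year denominators. The documents support none of these as a working assumption. Even the 1.2 to 1.3 above gives arm B no credit for late reports, and denominators of reportable person-time would remove the artefact.

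It also stands that second malignancy is not a listed endpoint, that the arms are not formally compared, and that Analysis VII specifies no comparison of second malignancies.

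**Conclusion.** The point holds as a flaw in safety ascertainment. Section 12.6 does not match the 7-year follow-up and makes any-cause reporting after year 5 depend on still being on maintenance. Followed exactly, it leaves malignancies judged unrelated or unlikely in patients off treatment without a clear reporting duty for up to 2 of 7 years, chiefly in untreated arm B patients.

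The size is modest: about 0.9 to 3.3 arm B cases outside the any-cause rule, and arm A appearing about 1.2 to 1.3 times higher at equal true risk. Both figures rest on the assumed malignancy rate, follow-up and retention, and the second also on full 7-year denominators. The effect is confined to descriptive safety summaries by group. The primary endpoint, at 12 months after randomization, is untouched. The change is worth making because the distortion runs along the treatment difference that the trial sets out to describe, and it costs little to remove.

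**What to change.** In 12.6, set one window for all patients: from informed consent to 7 years after registration, irrespective of arm, treatment status or progression, to match 10.1.1 and Analysis VII. Taking the start of treatment as registration, 15 cycles of 28 days are 420 days, or 1.15 years. Any-cause coverage of arm B after stopping would then rise from 5 − 1.15 = 3.85 to 7 − 1.15 = 5.85 years.

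The cost is one sentence in 12.6, the matching reporting instructions and a few more SAE forms. Because the 6-monthly visits in 10.1 stop at progression, second-malignancy status must also be asked at follow-up contacts after progression.

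If the 5-year window has already been applied, restrict every summary of second malignancies by group to the common first 5 years after registration, with person-time denominators. The price is that years 5 to 7 then contribute nothing to the comparison.

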12.7 Reporting of safety issues

The sponsor will promptly notify all concerned investigators, the Ethics Committee(s) (ECs) and the regulatory authorities of findings that could affect adversely the safety of patients, impact the conduct of the trial, increase the risk of participation or otherwise alter the ECs approval to continue the trial. In the occurrence of such an event the sponsor and the investigators will take appropriate urgent safety measures to protect the patients against any immediate hazard. The local investigator will inform the patients and local ethics or review committees according to hospital policy. The sponsor will inform any other parties that are involved in the trial.

12.8 Annual safety report

The sponsor will submit once a year a safety report to the ECs and Competent Authorities of the concerned Member States. The first report is sent one year after the first approval date of the trial. Subsequent reports are sent annually until end of trial. The content of the annual safety report will be according to the EU guidance document '*Detailed guidance on the collection, verification and presentation of adverse reaction reports arising from clinical trials on medicinal products for human use*'.

12.9 Data Safety and Monitoring Board (DSMB)

The DSMB will advise the Principal Investigator, co-investigators and the chair of the working group in writing about the continuation of the trial. The DSMB will review the general progress and feasibility of the trial, the quality and completeness of the data, adverse events and safety. The DSMB will consider if there is any concern regarding the safety and well-being of trial subjects or regarding the scientific validity of the trial results. The DSMB will base its advice on the reports provided by the statistician. The DSMB is free to take into consideration external information, such as the (interim) results of other trials or literature reports.

The DSMB consists of at least three members, with at least one statistician and two physicians. Details of the DSMB constitution and tasks are documented in the trial specific DSMB charter.

The DSMB will receive at least the following reports from the trial statistician for review:

- ◆ Interim analysis report (as described in 14.4.4)
- ◆ Annual safety data listing the incidence of (serious) adverse events, (serious) adverse reactions and SUSARs
- ◆ Annual progress data listing the number of enrolled patients and the status of data collection

The DSMB will meet or hold a telephone conference to discuss these reports.

12.10 Safety monitoring

The first 15 patients randomized to discontinue treatment (thus first 23 patients reaching MRD negativity, based on 1:2 randomization) will be evaluated by the investigators at time of MRD test after cycle 9, 12 and 15 and at 6 and 12 months for relapse or progression of CLL. Real time monitoring of the outcome for patients randomized for stopping treatment will continue based on the MRD results.

Also, an interim analysis on safety will be performed in the first 10 patients with CrCl between 30-50 ml/min.

In the event that a patient becomes MRD positive during the observation period, thorough written advice on the significance of the finding and further steps to be taken will be provided by the physicians at the central laboratory performing the MRD testing to the treating physician. This advice will contain information about the rationale for continuing within the protocol. Contact information to the physician at the central laboratory for further advice will be provided. Patients in the observation

arm becoming MRD positive $\geq 10^{-3}$ are retested one month later, if MRD positive at this time point $\geq 10^{-2}$, treatment with ibrutinib and venetoclax is reinitiated as detailed in section 9.

12.11 Product Complaints

A product quality complaint (PQC) is defined as any suspicion of a product defect related to manufacturing, labeling, or packaging, i.e., any dissatisfaction relative to the identity, quality, durability, or reliability of a product, including its labeling or package integrity. A PQC may have an impact on the safety and efficacy of the product. Timely, accurate, and complete reporting and analysis of PQC information from studies are crucial for the protection of subjects, investigators, and the sponsor, and are mandated by regulatory agencies worldwide.

- **Product complaint procedure for Ibrutinib.**

All initial PQCs must be reported to Janssen by the study-site personnel within 24 hours after being made aware of the event. If the defect is combined with a serious adverse event, the investigational staff must report the PQC to Janssen according to the serious adverse event reporting timelines within 24 hours of their knowledge of the event. A sample of the suspected product should be maintained for further investigation if requested by Janssen.

- **Product complaint procedure for venetoclax.**

AbbVie contact details for reporting Product Complaints:

[contact].

Please also inform the HOVON Data Center of your complaint by fax ([name]) or email ([contact]). Note that product complaints in and of themselves are not AEs. If a product complaint results in an SAE, an SAE form should be completed and sent to HOVON Data Center see section 12.3.1).

13 Endpoints

13.1 Primary endpoint

(Only considered for arm B of the study)

- ◆ Proportion of patients fulfilling the criteria for progression free survival (PFS) at 12 months after stopping therapy (27 months after starting treatment) for patients randomized to stop treatment. In this trial, reinitiated treatment due to MRD positivity will not be considered as progression, and symptomatic CLL according to IWCLL criteria within 12 months after randomization followed by reinitiation treatment resulting in a response (at least SD) before or at 12 months after randomization will neither be considered as progression.

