Secondary objectives (Arm B group)

- Time to and number of patients reinitiating treatment,
- Time to treatment failure after reinitiated treatment.

7 Study design

This study is designed as a phase 2 study with a late randomization in patients MRD negative after cycle 12 and 15, no formal comparisons between the two randomized treatment arms will be made.

During the treatment period all patients receive 15 cycles (28 days each) of oral ibrutinib + venetoclax treatment. During the first 2 cycles, only ibrutinib 420 mg a day is administered. From day 1 in cycle 3, ramp up over five weeks of venetoclax from 20 mg per day to the target of 400 mg per day is administered.

Patients achieving MRD negativity after cycle 12 in peripheral blood (PB) and at day 15 of cycle 15 in PB and bone marrow (BM) are randomized 1:2 between continuous ibrutinib treatment until toxicity or progression (arm A) and treatment free observation (arm B). Patients not reaching MRD negativity after cycle 12 and/or at day 15 of cycle 15 continue ibrutinib treatment until toxicity or progression (non-randomized patients).

MRD negative patients will be closely monitored for relapse/progression during the first 3 years after randomization by means of rapid reporting as described in section 16.1.1.

Patients becoming MRD positive (defined as $MRD \geq 10^{-3}$ and at least one month later $MRD \geq 10^{-2}$), or have symptomatic CLL according to IWCLL criteria (appendix A) during the observation period reinitiate treatment with both ibrutinib and venetoclax for 12 cycles and continue ibrutinib treatment until toxicity or progression.

Patients failing on reinitiating therapy (not reaching any response (CR/PR/SD) according to IWCLL criteria as assessed by the local investigator after 3 cycles of reinitiated therapy (or after reinitiation therapy until 12 months after randomization if progression occurred within 9 months from randomization) are considered as having progressive disease and will go off protocol treatment.

Details of all treatments (dose and schedule) are given in section 9.

8 Study population

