9.1 Treatment with ibrutinib and venetoclax

All patients should start protocol treatment (cycle 1, day 1), within 28 days after registration, or in case of new uncontrolled infection occurring after registration, when infection is under control.

All patients receive 15 cycles of ibrutinib + venetoclax (with ramp up and delayed start, see below). Each cycle has a duration of 28 days.

After 15 cycles of ibrutinib + venetoclax, subsequent treatment will be based on MRD status:

- Patients not achieving MRD negativity after cycle 12 (PB) AND/OR at day 15 of cycle 15 (PB+BM) continue on ibrutinib maintenance (non-randomized patients)
- Patients achieving MRD negativity after cycle 12 (PB) AND at day 15 of cycle 15 (PB+BM) are randomized 1:2 between ibrutinib maintenance (Arm A) and stopping treatment (observation) (Arm B).

Ibrutinib will be administered as a daily oral dosage of 420 mg (3 x 140 mg) starting on day 1 of cycle 1.

Venetoclax administration starts in cycle 3. Assessment of subject-specific factors for level of risk of TLS and providing prophylactic hydration and anti-hyperuricemics to subjects prior to first dose of venetoclax to reduce risk of TLS is mandatory (see appendix G). Venetoclax will be administered orally once daily beginning with a dose ramp-up period. The initial venetoclax dose is 20 mg. After one week of treatment at 20 mg, the dose will be escalated to 50 mg, followed by subsequent increases, each after one week, to 100 mg, 200 mg and the maximum dose of 400 mg. The 5-week ramp-up dosing schedule is designed to gradually reduce tumor burden (debulk) and decrease the risk of TLS.

Patients with a high tumor burden or assessed as high risk for TLS at baseline, should be re-assessed for TLS risk, at the end of cycle 2 (before venetoclax ramp up) including a CT-scan,

absolute leucocyte count (ALC) and creatinine clearance (CrCl, directly measured with 24hr urine collection or calculated according to the modified formula of Cockcroft and Gault, appendix E).

For patients with CrCL between 30-50 ml/min , inclusion in the trial is acceptable if:

- ◆ CrCl and ALC count will be re-assessed at end of cycle 2 (before venetoclax ramp up)
- ◆ Upon significant (above 15%) creatinine increase, treatment will be put on hold for a work up by a nephrologist to assess whether treatment can be reinitiated
- ◆ Re-assessment with a CT scan will be performed at end of cycle 2
(using contrast is up to local investigator based on kidney function)

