14.1 Patient numbers and power considerations

Treatment arms will be analyzed separately, only observation arm (arm B) will be considered for the primary end point. Only patients who are MRD negative after induction (i.e. MRD negative at both cycle 12 and at day 15 of cycle 15) will be randomized 1:2 for ibrutinib until progression (arm A) versus observation arm (arm B). It is expected that 45% of the registered patients will be randomized, based on the hitherto reported MRD negativity rates for venetoclax monotherapy and combination therapy with rituximab and the reported preclinical data on synergy between venetoclax and ibrutinib. The power calculation is based on the observation arm, at least equal or even better PFS is expected for the patients randomized for ibrutinib until progression. Patients who are MRD positive continuing on maintenance ibrutinib are expected to have a lower PFS than MRD negative patients.

The observation arm B is considered valuable if the PFS at 12 months after randomization is at least 75%. A success rate of less than 60% is considered not valuable for further investigation (in Phase III setting); this assumption is based on a 1-year PFS of 60% for RR CLL patients treated with FCR for the PFS endpoint (Fornecker, Am J Hem, 2015). No interim analysis on the primary endpoint is planned. An A'Hern one-stage design is used for the sample size calculation.

- Let P_0 be the largest success rate which, if true, implies that the therapeutic activity is too low and therefore does not warrant further investigation,. In the present trial, P_0 has been taken as 60%.
- Let P_1 be the smallest success rate which, if true, implies that the therapeutic activity is sufficiently high and therefore warrants further investigation in clinical trials. In the present trial, P_1 has been taken as 75%.

In order to reject the null hypothesis $H_0: P = P_0$ in favor of the alternative hypothesis $H_1: P = P_1$ with power $1 - \beta = 0.80$ (1-sided significance level $\alpha = 0.05$), 62 (eligible) patients are required in maintenance treatment arm with observation until progression (and at least 44 patients progression free at 12 months after randomization).

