14.4 Statistical analysis

14.4.1 Efficacy analysis

The PFS primary endpoint will be analyzed as soon as all randomized patients have achieved the landmark of 12 months after randomization. Thus, final analysis will take place as soon as the last patient starting treatment has reached the time point month 27 and data have been assembled from all study sites. Giving an estimated 3 years recruitment period, time point of final PFS analysis is projected 5 years and 6 months after trial initiation.

The primary efficacy endpoint is the investigator-assessed proportion of patients with PFS at month 27 in arm B, the ITT population for arm B is used for calculation of the proportion. PFS is defined as all patients free of progression or relapse (determined using standard IWCLL guidelines [2008], appendix A), or death from any cause, whichever occurs first. Patients in the observation arm becoming MRD positive thus restarting treatment are still considered progression free, as long as they don't progress according to IWCLL criteria after start reinitiation treatment. If patients in the observation arm have clinical progression but achieve response within three months of reinitiating treatment, they are still considered progression free. For patients reinitiating therapy before 27 months according to the rules outlined above who have progressed according to IWCLL criteria before reinitiating treatment are allowed up to 3 months after reinitiating therapy to obtain response. These patients will be considered progression free at month 27 if a response is achieved within 3 months from reinitiating therapy.

The primary objective of the study is to test the following hypothesis:

The progression free survival rate at 12 months after randomization for the observation arm (B) is more than 60% (i.e., H_0 : PFS rate at 12 months post-randomization \leq 60% versus H_1 : PFS rate at 12 months post-randomization $>$ 60%). PFS and the 95% confidence interval (CI) will be estimated using Kaplan-Meier survival methodology, and a Kaplan-Meier survival curve will be generated to

provide a visual illustration of PFS for patients in the different treatment arms separately (from randomization), and also for all patients together (from registration).

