15.3 Randomization

Patients achieving MRD negativity after cycle 12 (peripheral blood) and at day 15 of cycle 15 (peripheral blood and bone marrow), are randomized between continuous ibrutinib treatment until toxicity or progression and treatment free observation. Patients not reaching MRD negativity are not randomized and continue ibrutinib treatment until toxicity or progression.

Randomization has to occur within 14 days after MRD testing after day 15 of cycle 15.
Patients need to be randomized at the HOVON Data Center as described above for registration.

The following information will be requested at randomization:

- ◆ Protocol number
- ◆ Institution name
- ◆ Name of caller/responsible investigator
- ◆ Patient study number
- ◆ Response after cycle 12 and cycle 15

Patients will be randomly assigned to maintenance ibrutinib or observation arms through 1:2 randomization process with stratification at randomization by center, comorbidity (CIRS ≤ 6 vs >6), and TP53 aberration (TP53 mutation and or del(17p), no vs yes) with a minimization procedure, ensuring balance within each stratum and overall balance.

Result of randomization will be given immediately by TOP or phone and confirmed by fax or email.

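### Fifteen 28-day cycles end at month 13.8, so month 27 is not 12 months after stopping and the primary endpoint carries two dates about five weeks apart

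*Protocol*

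**What the plan says.** The length of induction is fixed. Section 7 says that "all patients receive 15 cycles (28 days each) of oral ibrutinib + venetoclax treatment", and section 9.1 repeats: "Each cycle has a duration of 28 days". Section 15.3 ties randomization to the last MRD sample: "Randomization has to occur within 14 days after MRD testing after day 15 of cycle 15".

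The date of the primary endpoint is given in several places:

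- **Section 13.1** sets it "at 12 months after stopping therapy (27 months after starting treatment". In the same paragraph, symptomatic disease followed by a response to reinitiated treatment "before or at 12 months after randomization will neither be considered as progression".
- **Section 14.1** gives the decision rule for 62 patients as "at least 44 patients progression free at 12 months after randomization".
- **Section 14.4.1** defines the endpoint as the "investigator-assessed proportion of patients with PFS at month 27 in arm B". It then states the hypothesis as "The progression free survival rate at 12 months after randomization for the observation arm (B) is more than 60" per cent. It triggers the analysis when all randomized patients reach 12 months after randomization, and presents month 27 as following from that.

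Elsewhere, induction is counted as 15 months. Section 10.1 reaches month 51 by adding 3 years to 15 months, and section 16.1.1 gives 15 months of ibrutinib reporting for patients who stop. Table 10.2.1 schedules CT and bone marrow at day 15 of cycle 15 and at month 27. Section 10.4 makes the 3-monthly response evaluations clinical, without CT.

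**The concern.** Fifteen cycles appear to have been counted as fifteen calendar months. If so, two descriptions that the protocol treats as one date are different dates, and the confirmatory analysis uses both: one to define the proportion, the other to state the hypothesis and the success threshold. The test compares a count with 44, so a few patients whose event falls between the dates could decide the result. The CT and marrow that should support the endpoint may also come after the date being tested.

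**Working it through.** **Inputs.** 15 cycles of 28 days (sections 7 and 9.1); randomization within 14 days of the cycle 15 day 15 sample (15.3); P0 60%, P1 75%, one-sided alpha 0.05, power 0.80, n = 62, at least 44 successes (14.1). One calendar month is 365.25/12 = 30.44 days.

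**1. The stated design.** Exact binomial with n = 62 and at least 44 successes:

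- P(X ≥ 44 | 0.60) = 0.049
- P(X ≥ 44 | 0.75) = 0.812

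This reproduces the plan, and 62 is the smallest n that meets both limits.

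**2. Length of induction.** 15 × 28 = 420 days; 420/30.44 = 13.8 months.

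**3. Twelve months after stopping.** 420 + 365.25 = day 785, and 785.25/30.44 = month 25.8. Month 27 is 27 × 30.44 = day 822. The gap is 37 days, so month 27 is 13.2 months after stopping.

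**4. Twelve months after randomization.** Cycle 15 day 15 is treatment day 14 × 28 + 15 = 407, so the window runs from day 407 to day 421.

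| Randomization | 12-month landmark | Gap to month 27 | Month 27, in months after randomization |
|---|---|---|---|
| Day 421 (end of cycle 15) | day 786, month 25.8 | 36 days | 13.2 |
| Day 407 (day of sampling) | day 772, month 25.4 | 50 days | 13.6 |

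**5. Who is affected.** A patient who dies, or progresses without rescue, between the two dates is a success at 12 months after randomization and a failure at month 27. A progression in the gap that then responds need not differ, because section 14.4.1 allows up to 3 months after reinitiation for a response and still counts the patient as progression free.

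**6. Size, if month 27 were the date tested.** The documents give no hazard. Assume a constant hazard with 60% and 75% holding at exactly 12 months; the rate at t months is then p^(t/12).

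| t (months) | From 75% | Power of 44/62 | From 60% | P(X ≥ 44) |
|---|---|---|---|---|
| 12.0 | 75.0% | 0.81 | 60.0% | 0.049 |
| 13.2 | 72.9% | 0.69 | 57.0% | 0.017 |
| 13.6 | 72.1% | 0.64 | 56.0% | 0.011 |

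**7. Month 51.** Three years after stopping is (420 + 1095.75)/30.44 = month 49.8. Month 51 is 3.1 years after stopping.

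**The case against.** The best defence is that month 27 is a nominal label, 15 plus 12. The protocol does use cycles and months loosely: the synopsis gives reinitiated combination treatment as 12 cycles in one row and 12 months in another, and the time allowed for a response is 3 cycles in section 9.4 but three months in section 14.4.1. In Table 10.2.1 the extra columns seem to add tests to scheduled visits, so the extra at month 27 may simply be the 12-month visit with CT and marrow. This defence stands in part: it cannot be said with certainty that these are two separate visits. It does not remove the contradiction, because section 13.1 spells the label out as time since starting treatment and section 10.1 adds three calendar years to it. Reading a month as 28 days does not help either: 12 such months are 336 days, or 11.0 calendar months, while P0 in section 14.1 rests on a 1-year rate.

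It can also be said that interruptions lengthen induction. Under Appendix H, ibrutinib holds of up to 28 days return to the original schedule with missed doses skipped. Longer holds are possible, however, and Appendix I allows ramp-up steps to be repeated. The gap is therefore the planned one, and may be narrower for some patients. The 50-day extreme is also unlikely: section 10.6 allows a week for MRD results and section 8.2 requires a response after cycle 15, so randomization near the end of the cycle is more plausible.

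A reader might infer that the trial has only 64% to 69% power, or a true type I error near 1.7%. The documents do not support that. The hypothesis and the 44/62 rule are stated at 12 months after randomization, where the design figures are right. A test of a rate of at most 60% with this rule has size 4.9% at whichever date the rate is measured, and power 81% if 75% is the rate at that date. The other figures need month 27 as the tested date, a constant hazard, and 60% and 75% true at exactly 12 months.

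Visit windows are often left to a statistical analysis plan. The choice of date is not: section 14.4.6 says that deviations settled there cannot affect the primary analysis.

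**Conclusion.** The point holds. On the planned schedule, equating 12 months after stopping with 27 months after starting is wrong by about 37 days, and section 14.4.1 defines the primary proportion at one date and tests it at another. Counted from randomization the gap is about 36 days, and up to 50 only in the extreme case. What differs between the wordings is the classification of deaths and unrescued progressions in that interval; the protocol does not give their number. If month 27 is applied as a calendar date, the scheduled CT and marrow fall after the tested landmark.

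The sample size and threshold are not at fault. Any loss of power, to about 69% at 13.2 months, is conditional on the assumptions in step 6, and the shift is conservative for type I error. It needs correcting because a confirmatory endpoint must have one date.

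**What to change.** State one anchor, 12 months after randomization with a visit window, and use it for the primary endpoint (synopsis, sections 6, 13.1 and 14.4.1), for the CT, marrow and MRD assessment now labelled month 27 (sections 10.4 and 10.6, Tables 10.2.1 to 10.2.3), and for the final-analysis trigger (14.4.1 and Analysis VI in 14.4.4). For non-randomized patients, count from the end of cycle 15. Re-express month 51 as 36 months after the same anchor. Delete the statement that the landmark is 27 months after starting treatment, or mark it as a nominal visit label.

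The cost is an amendment to wording and the visit calendar. No patients or visits are added, and n = 62 with a threshold of 44 remains valid.
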